10.5. Appendix 5: Data Display Standards & Handling Conventions

10.5.1. Study Treatment & Sub-group Display Descriptors

Treatment Group Descriptions			
Study Group		Data Displays for Reporting	
Code	Description	Description	Order ^[1]
A	CAB PO 30 mg QD	CAB 30 mg	1
B	CAB LA IM 600 mg Q8W	CAB LA 600 mg	2

NOTES:

- Order represents treatments being presented in TFL, as appropriate.

10.5.2. Baseline Definition & Derivations

10.5.2.1. Baseline Definitions

The baseline or pre-dose assessment is the last available assessment prior to the time of the first dose unless it is specified otherwise.

10.5.2.2. Derivations and Handling of Missing Baseline Data

Definition	Reporting Details
Change from Baseline	= Post-Dose Visit Value – Baseline
% Change from Baseline	= 100 x [(Post-Dose Visit Value – Baseline) / Baseline]
Maximum Change from Baseline	= Calculate the change from baseline at each given timepoint and determine the maximum change

NOTES:

- Unless otherwise specified, the baseline definitions specified in Section 10.5.2.1 Baseline Definitions will be used for derivations for endpoints / parameters and indicated on summaries and listings.
- Unless otherwise stated, if baseline data is missing no derivation will be performed and will be set to missing.
- The baseline definition will be footnoted on all change from baseline displays.

10.5.3. Reporting Process & Standards

Reporting Process
Software

 The currently supported versions of SAS software 9.2 or higher and Phoenix WinNonlin will be used.
Analysis Datasets

 Analysis datasets will be created according to CDISC standards SDTMIG v3.2 & ADaMIG v1.0 For creation of ADaM datasets (ADCM/ADAE), the same version of dictionary datasets will be implemented for conversion from SI to SDTM.

Reporting Process	
Generation of RTF Files	

 RTF files will be generated for the TLFs. But only compiled PDF file will be used in the delivery. 	
Reporting Standards	
General	

 The current GSK Integrated Data Standards Library (IDSL) will be applied for reporting, unless otherwise stated: 
 4.03 to 4.23: General Principles 5.01 to 5.08: Principles Related to Data Listings 6.01 to 6.11: Principles Related to Summary Tables 7.01 to 7.13: Principles Related to Graphics 	
Formats	

 All data will be reported according to the actual treatment the subject received unless otherwise stated. GSK IDSL Statistical Principles (5.03 & 6.06.3) for decimal places (DP's) will be adopted for reporting of data based on the raw data collected. Numeric data will be reported at the precision collected on the eCRF. The reported precision from non eCRF sources will follow the IDSL statistical principles but may be adjusted to a clinically interpretable number of DP's 	
Planned and Actual Time	

 Reporting for tables, figures and formal statistical analyses : 
 Nominal visits collected on the eCRF will be used in figures, summaries, statistical analyses and calculation of any derived parameters, unless otherwise stated. The impact of any major deviation from the planned assessment times and/or scheduled visit days on the analyses and interpretation of the results will be assessed as appropriate. Reporting for Data Listings: 
 Planned and actual time relative to study drug dosing will be shown in Pharmacokinetic listings (Refer to IDSL Statistical Principle 5.05.1). Unscheduled or unplanned readings will be presented within the subject's listings. Visits outside the protocol defined time-windows (i.e. recorded as protocol deviations) will be included in listings but omitted from figures, summaries and statistical analyses. 	
Unscheduled Visits	

 Unscheduled visits will not be included in summary tables. Unscheduled visits will not be included in figures. All unscheduled visits will be included in listings. 	
Descriptive Summary Statistics	
Continuous Data	Refer to IDSL Statistical Principle 6.06.1
Categorical Data	N, n, frequency, %
Reporting of Pharmacokinetic Concentration Data	
Descriptive Summary Statistics	Refer to IDSL Statistical Principle 6.06.1 Assign zero to NQ values (Refer to GUI_51487 for further details)

Reporting Standards	
Reporting of Pharmacokinetic Parameters	

 Reporting for PK tables, figures and listings: 
 Planned time relative to dosing will be used in mean concentration-time figures and summaries, and actual times will be used for individual concentration-time figures. The impact of any major deviation from the planned assessment times and/or scheduled visit days on the analyses and interpretation of the results will be assessed as appropriate. Visits outside the protocol defined time-windows (i.e. recorded as protocol deviations) will be included in all PK figures, summaries and listings. 	
Descriptive Summary Statistics (Log Transformed)	N, n, geometric mean, 95% CI of geometric mean, standard deviation (SD) of logged data and [between and or within] geometric coefficient of variation (CV _b (%)) will be reported. $CV_b (\%) = \sqrt{(\exp(SD^2) - 1) * 100}$ (SD = SD of log transformed data)
Parameters Not Being Log Transformed	tmax, first point, last point, and number of points used in the determination of λz.
Summary Tables	The following PK parameters will not be summarised: first point, last point, and number of points used in the determination of λz
Listings	Additionally, include the first point, last point and number of points used in the determination of lambda_z for listings.
Graphical Displays	

 Refer to IDSL Statistical Principals 7.01 to 7.13. 	

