7. PRIMARY STATISTICAL ANALYSES

7.1. Safety Analyses of CAB LA

Four study phases are defined for this study: screening phase, oral phase, injection phase and follow-up phase (see [Appendix 4](#) for the definition of each phase).

The primary safety analysis will be conducted after all ongoing participants complete the Week 41 visit and datasets have been authorized. All data from injected participants collected from Week 5 to Week 41 (i.e., in the injection phase) will be analysed. Analysis endpoints will include Grade 2 or higher clinical and laboratory events that occur from the initial injection to 8 weeks after the last injection among participants who receive at least one injection.

The extended safety analysis will be conducted after all ongoing participants complete the Week 89 visit and datasets have been authorized. All data from injected participants collected from Week 5 to Week 89 (i.e., in the injection phase and the follow-up phase) will be analysed. Analysis endpoints are the same as in the primary safety analysis.

To assess safety, the number and the percent of participants experiencing each safety endpoint will be tabulated. Each participant will contribute once in each category (i.e., only for the highest severity AE) for the evaluation of safety.

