7.1.3. Clinical Laboratory Tests

All clinical laboratory tests will be graded according to the [Appendix 7](#) from the study protocol. Grade 2 or higher laboratory events will be tabulated by number and percentage of subjects with the event by study phase.

Change from baseline in hematology, fasting chemistry, fasting lipid profile, and coagulation profile will be summarized by visit. For the definition of baseline, refer to Section [10.5.2](#). Urinalysis and urine chemistry results will be summarized by visit as either categorical values or as continuous values, depending on the type of the parameter.

For each lab test, shift from baseline table will be provided based on toxicity grade, both by visit and for the shift to maximum toxicity grade in each study phase. Data collected at unscheduled visits will not be included in the by-visit summary, but will be used in the calculation of maximum grade in each study phase. Subjects having both high and low values will be counted in both High and Low categories for the summary by study phase.

All lab data, as well as lab data for subjects with Grade 2 or higher abnormalities, will be listed. Abnormal data will be listed with an indicator, which is low/high relative to normal range. All laboratory results from local labs, if any, will be listed only

[Table 5](#) provides an overview of the planned lab test analyses, with full details of data displays being presented in [Appendix 14](#): List of Data Displays.

Table 5 Overview of Planned Lab Test Analyses

Display Type	Absolute				Change from Baseline			
	Summary		Individual		Summary		Individual	
	T	F	F	L	T	F	F	L
Laboratory Test Analyses								
Grade 2 or high laboratory events	Y							
Clinical Chemistry				Y	Y			
Hematology				Y	Y			
Fasting Lipid Profile				Y	Y			
Coagulation Profile				Y	Y			
Urinalysis and Urine Chemistry	Y			Y	Y			
Other lab data including local lab				Y				

- T = Table, F = Figure, L = Listing, Y = Yes display generated.
- Stats Analysis = Represents TFL related to any formal statistical analyses (i.e. modelling) conducted.
- Summary = Represents TFL related to any summaries (i.e. descriptive statistics) of the observed raw data.
- Individual = Represents FL related to any displays of individual subject observed raw data.

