10.3. Appendix 3: Assessment Windows**10.3.1. Assessment Windows**

The nominal visit information collected on CRF will be used in the analysis. Analysis visit based on the time window will not be defined in this study.

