10.6. Appendix 6: Derived and Transformed Data

10.6.1. General

Multiple Measurements at One Time Point

- If there are two values within a time window the value closest to the target day for that window will be used. If values are the same distance from the target then the mean will be taken.
- Subjects having both High and Low values for Normal Ranges at any post-baseline visits for safety parameters will be counted in both the High and Low categories of “Any visit post-baseline” row of related summary tables. This will also be applicable to relevant Potential Clinical Importance summary tables.

Study Day

- Calculated as the number of days from Day 1 Visit:
 - Ref Date = Missing → Study Day = Missing
 - Ref Date < Date of Day 1 Visit → Study Day = Ref Date – Date of Day 1 Visit
 - Ref Date ≥ Date of Day 1 Visit → Study Day = Ref Date – Date of Day 1 Visit + 1

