24	Safety		Listing of Death		W41 SAC [1], SAC [1]
Laboratory Tests					
25	Safety	LB5	Listing of Chemistry Data and Fasting Lipid Profile		W41 SAC [1], SAC [1]
26	Safety	LB5	Listing of Hematology and Coagulation Data		W41 SAC [1], SAC [1]
27	Safety	UR2a	Listing of Urinalysis and Urine Chemistry Data		W41 SAC [1], SAC [1]
28	Safety	LB5	Listing of Laboratory Data for Subjects with Grade 2 or Higher Abnormalities		W41 SAC [1], SAC [1]
29	Safety	LB14	Listing of HIV Tests		W41 SAC [1], SAC [1]
30	Safety	LB5	Listing of Local Lab Data		W41 SAC [1], SAC [1]

ICH: Listings					
No.	Population	IDSL / TST ID / Example Shell	Title	Programming Notes	Deliverable [Priority]
Vital Sign					
31	Safety	VS4	Listing of Vital Signs		W41 SAC [1], SAC [1]
32	Safety	VS4	Listing of Vital Signs for Subjects with Any Value of Potential Clinical Importance		W41 SAC [1], SAC [1]
ECG's					
33	Safety		Listing of ECG Results		W41 SAC [1], SAC [1]
Social Harm					
34	Safety		Listing of Social Harm		W41 SAC [1], SAC [1]
Cardiovascular Event					
35	Safety		Listing of Cardiovascular Event		W41 SAC [1], SAC [1]
Liver Event					
36	Safety		Listing of Liver Event		W41 SAC [1], SAC [1]
Tolerability of CAB Injection					
37	Safety Injection		Listing of HIV-Prevention Treatment Satisfaction Questionnaire		W41 SAC [1], SAC [1]

ICH: Listings					
No.	Population	IDSL / TST ID / Example Shell	Title	Programming Notes	Deliverable [Priority]
Acceptability of the CAB Injection					
38	Safety		Listing of Acceptability of the CAB LA		W41 SAC [1], SAC [1]
Pharmacokinetic					
39	Oral PK	PKCL1P	Listing of CAB Plasma Pharmacokinetic Concentration-Time Data – Oral Phase	Please list all the concentration data including unscheduled.	SAC [1]
40	Oral PK	PKPL1P	Listing of Derived CAB Plasma Pharmacokinetic Parameters – Oral Phase		SAC [1]
41	Injection (Week 41) PK	PKCL1P	Listing of CAB Plasma Pharmacokinetic Concentration-Time Data – Injection Phase (up to Week 41)	Please list all the concentration data including unscheduled.	W41 SAC [1], SAC [1]
42	Injection (Week 41) PK	PKPL1P	Listing of Derived CAB Plasma Pharmacokinetic Parameters – Injection Phase (up to Week 41)		W41 SAC [1], SAC [1]
43	Injection (Week 89) PK	PKCL1P	Listing of CAB Plasma Pharmacokinetic Concentration-Time Data – Injection Phase (up to Week 89)	Please list all the concentration data including unscheduled.	SAC [1]

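### SAP 10.5.3 leaves out-of-window safety visits out of the tables while SAP 7.1 analyses all Week 5 to 41 data, and the protocol's in-window PK concentration summary is missing without a declared change

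*SAP*

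**What the plan says.** **Safety data.** Under its sub-heading on data listings, SAP 10.5.3 says: "Visits outside the protocol defined time-windows (i.e. recorded as protocol deviations) will be included in listings but omitted from figures, summaries and statistical analyses". The windows meant are the protocol's visit tolerances of ±3 days (Protocol Table 1, footnote q; repeated under SAP Table 21). A few lines earlier, for tables, figures and formal analyses, the same section says: "Nominal visits collected on the eCRF will be used in figures, summaries, statistical analyses and calculation of any derived parameters, unless otherwise stated". A later part of 10.5.3 reverses the omission for PK figures, summaries and listings. No such reversal is given for safety.

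Other SAP sections bear on the same results:

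- SAP 7.1, primary safety analysis: "All data from injected participants collected from Week 5 to Week 41 (i.e., in the injection phase) will be analysed".
- SAP 10.3.1: "Analysis visit based on the time window will not be defined in this study".
- SAP 10.5.3 on unscheduled visits: "Unscheduled visits will not be included in summary tables".
- SAP 7.1.3, on unscheduled laboratory data: these stay out of the by-visit summary "but will be used in the calculation of maximum grade in each study phase".

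**PK concentrations.** Protocol 10.3.1.2 asks for concentrations to be summarised twice: once with all data whatever their timing, and once with evaluable data inside allowable windows that the analysis plan is to define. SAP 10.14.8 lists one concentration summary per phase (Tables 3.1, 3.4 and 3.9). SAP 2.1, which records changes from the protocol, mentions only the adverse events of special interest.

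**The concern.** Two statements in the SAP give different answers to a simple programming question: does a scheduled laboratory or vital-sign result taken 4 days off target go into the tables? SAP 7.1 says yes without qualification. SAP 10.5.3 says no, and because it spells out an exception for PK and none for safety, a programmer could reasonably conclude that the omission applies to safety.

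At stake is the completeness of the primary safety tables, which include Grade 2 or higher laboratory events. The literal rule also gives an odd ordering. An unscheduled laboratory result would count toward the maximum grade, while a planned result taken a day beyond the window would not.

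The PK limb is different in kind. A summary that the protocol specifies for a primary objective would be absent from the report, with nothing in the list of changes to tell the reader.

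**Working it through.** No sample-size or power figure is involved. The check is a comparison of texts, followed by a count of the results exposed.

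**1. What each text does with a laboratory result from the injection phase**

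| Text | Scheduled, 4 days off target | Unscheduled |
|---|---|---|
| SAP 7.1 | analysed | analysed |
| SAP 10.5.3, nominal-visit bullet | used under its nominal label, subject to exceptions stated elsewhere | not addressed |
| SAP 10.5.3, omission sentence | listed only | not addressed |
| SAP 10.5.3, unscheduled rule | not addressed | not in summary tables |
| SAP 7.1.3 | not addressed | not in by-visit tables; counts toward maximum grade per phase |

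The first column holds the unresolved conflict, between 7.1 and the omission sentence. In the second column 7.1.3 settles the matter for laboratory grades, because it is the more specific text.

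**2. Displays affected under the literal reading**

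- Laboratory: Table 2.16 (Grade 2 or higher), Tables 2.18 to 2.20 (by visit) and Tables 2.21 to 2.23 (grade shifts).
- Vital signs: Tables 2.24 and 2.25.
- Not affected: adverse event tables, because SAP 10.4.2.1 assigns events by start date.
- Still visible: Listings 25 to 27 for all laboratory data, Listing 28 ("Listing of Laboratory Data for Subjects with Grade 2 or Higher Abnormalities"), and Listings 31 and 32 for vital signs.

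**3. Number of scheduled results exposed**

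Inputs: about 40 participants entering the injection phase (Protocol 5.2), and visits from Protocol Table 1, assuming full follow-up.

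- Haematology and chemistry at Weeks 5, 6, 9, 17, 25, 33 and 41: 40 × 7 = 280 panels. Without Week 5, the day of the first injection, 40 × 6 = 240.
- Vital signs at 12 injection-phase visits: 40 × 12 = 480 sets.
- Lipids, coagulation and urinalysis: one scheduled post-baseline time, Week 41, so 40 × 1 = 40 of each.

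The number lost would be these totals multiplied by the out-of-window rate, which the documents do not give. As an illustration only, assumed rates of 2% to 15% would remove 280 × 0.02 = 5.6 to 280 × 0.15 = 42 chemistry panels, and 480 × 0.02 = 9.6 to 480 × 0.15 = 72 vital-sign sets. They would leave 40 × 0.02 = 0.8 to 40 × 0.15 = 6 participants with no scheduled post-baseline lipid, coagulation or urinalysis result in any table. The conflict does not depend on these rates.

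**4. The PK summary**

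- Required by Protocol 10.3.1.2: an all-data summary, an in-window summary, and windows defined in the analysis plan.
- Present in the SAP: scheduling tolerances (±3 days; 20 to 28 hours for the oral trough; ±15 minutes for intensive sampling), none of them named as the allowable window, and one concentration table per phase.
- Declared in SAP 2.1: nothing on this.

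Would the two summaries differ much? Protocol 5.5 gives a simulated median trough of 1.35 µg/mL, falling to 1.08 µg/mL with a one-week delay. Suppose every out-of-window trough were 7 days late, at the same assumed rates. The geometric mean would then shift by exp(p × ln(1.08/1.35)) − 1, which is −0.4% at p = 0.02 and −3.3% at p = 0.15. For comparison, with n = 40 and a between-subject CV of 42% (Protocol Table 3, 8-weekly regimen in HIV-infected participants), the SD on the log scale is √ln(1 + 0.42²) = 0.403. The 95% interval is then exp(±2.023 × 0.403/√40) − 1, or −12% to +14%. The shift is small beside that.

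**The case against.** A reader might infer that 10.5.3 flatly contradicts itself. The documents do not show that. The nominal-visit bullet allows for exceptions, and the omission sentence can be read as one. But that makes the literal reading more plausible and leaves the conflict with 7.1 in place.

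Nor does SAP 10.3.1 clearly conflict. It says that visits keep their nominal labels and are not remapped, which is compatible with dropping some of them. The unscheduled-visit rule and 7.1.3 are a general convention and a specific exception, which an analyst would resolve in favour of 7.1.3.

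The strongest defence is that SAP 10.4.1 assigns assessments as well as events to phases by date, and 7.1.3 tabulates Grade 2 or higher laboratory events by phase. Since unscheduled results count toward maximum grade, excluding planned ones would be incoherent, so a sensible team would include them. This has weight for the phase-based tables and less for the by-visit ones. Even so, assigning a result to a phase does not say whether it is tabulated, and the omission sentence covers summaries without distinction.

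Two further points stand. Protocol 9.4.7 requires clinically relevant laboratory changes to be recorded as adverse events, so these would also reach the unaffected tables. And Protocol 10.3 lets the analysis plan settle what is tabulated, so the safety limb is an internal inconsistency and not a departure from the protocol.

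On PK, the SAP openly includes out-of-window visits in its PK summaries, and detailed display specifications are available only on request. That supports the all-data summary. It does not supply the second one or its windows.

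**Conclusion.** The point holds in two limited parts, and both should be corrected.

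**Safety.** SAP 10.5.3 and SAP 7.1 conflict on scheduled results outside ±3 days, and the SAP does not say which prevails. If 10.5.3 were followed, those laboratory and vital-sign results would be missing from the tables, with Week 41 lipids, coagulation and urinalysis most exposed. The size is unknown because no out-of-window rate is given. It would be wrong to conclude that safety findings would be concealed: the results remain in several listings, and adverse event tables do not change.

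**PK.** The in-window concentration summary required by Protocol 10.3.1.2 is not planned, its windows are not defined, and the change is not declared in SAP 2.1. A reader might infer that the trough estimates are biased. The illustration above gives no support for that, within its assumed rates and 7-day delay.

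One might also suspect that out-of-window troughs are excluded from the accumulation and steady-state models, since the PK exception does not name statistical analyses. SAP 7.3.3.1 largely answers this: all concentrations enter parameter estimation whatever their timing, and study-team review of deviations is the only stated route to exclusion.

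**What to change.** 1. **Safety data.** Delete the omission sentence for safety data in SAP 10.5.3. State that scheduled visits are summarised under their nominal label whatever their timing. Count all post-baseline central-laboratory results, out-of-window and unscheduled included, in the Grade 2 or higher and maximum-grade tables. Say that 7.1.3 governs there and that local-laboratory results remain listed only, as 7.1.3 already provides.
2. **PK concentrations.** Either define the allowable sampling windows and add in-window versions of Tables 3.1, 3.4 and 3.9, or record in SAP 2.1 that the in-window summary is dropped.
3. **Optional clarifications.** Confirm in SAP 7.3.3.2 that the models use all trough values retained after deviation review. Reword SAP 10.6.1 ("If there are two values within a time window the value closest to the target day for that window will be used"), since the SAP defines no analysis windows.

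The cost is a few lines of SAP wording and at most three extra tables, with no new data. The in-window tables would rest on slightly fewer observations than the all-data ones.

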10.3. Statistical Analyses

The primary safety analysis and PK analyses including both oral phase and injection phase through Weeks 5 to 41 will be performed after all ongoing participants complete the Week 41 visit and datasets have been authorized. Other secondary analyses as mentioned, where appropriate, will also be performed. The end of study analysis will be performed after all ongoing participants complete the Week 89 visit.

Data will be listed and summarized according to GSK reporting standards, where applicable. Listings will be sorted by participant, study period or phase, visit, actual study day, and time if applicable. Summary tables and figures will be presented by visit and time if applicable.

The baseline or pre-dose assessment is the last available assessment prior to the time of the first dose unless it is specified otherwise. If there are multiple assessments collected at the same scheduled time, the average of these assessments will be used. For tabulated safety summaries, only the scheduled assessments will be included in the summary tables or as noted in the Reporting and Analysis Plan (RAP).

Complete details of the planned analysis will be documented in the RAP.

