12.6. Appendix 6: Liver Safety: Required Actions and Follow-up Assessments

Phase 1 Liver chemistry stopping criteria have been designed to assure participant safety and to evaluate liver event etiology (in alignment with FDA premarketing clinical liver safety guidance).

<http://www.fda.gov/downloads/Drugs/GuidanceComplianceRegulatoryInformation/Guidances/UCM174090.pdf>

Phase 1 liver chemistry stopping criteria and required follow up assessments

Liver Chemistry Stopping Criteria	
ALT-absolute	
ALT\geq3xULN
 
If ALT\geq3xULN AND bilirubin^{1,2} \geq 2xULN (>35% direct bilirubin) or INR >1.5, Report as an SAE.
 
See additional Actions and Follow Up Assessments listed below

Required Actions and Follow up Assessments	
Actions	Follow Up Assessments

 • Immediately discontinue study treatment • Report the event to GSK within 24 hours • Complete the liver event CRF, and complete an SAE data collection tool if the event also meets the criteria for an SAE² • Perform liver event follow up assessments • Monitor the participant until liver chemistries resolve, stabilize, or return to within baseline (see MONITORING below) 
MONITORING:
 
If ALT\geq3xULN AND bilirubin \geq 2xULN or INR >1.5
 
 • Repeat liver chemistries (include ALT, AST, alkaline phosphatase, bilirubin) and perform liver event follow up assessments within 24 hrs • Monitor participants twice weekly until liver chemistries resolve, stabilize or return to within baseline • A specialist or hepatology consultation is 	
 • Viral hepatitis serology³ • Obtain INR and recheck with each liver chemistry assessment until the transaminases values show downward trend • A blood sample for pharmacokinetic (PK) analysis will be obtained at every visit, and therefore, should be available to match with Liver Function Test (LFT) findings. An additional PK sample should be obtained at the same time as any unscheduled LFT assessment. • Serum creatine phosphokinase (CPK) and lactate dehydrogenase (LDH). • Fractionate bilirubin, if total bilirubin\geq2xULN • Obtain complete blood count with differential to assess eosinophilia • Record the appearance or worsening of clinical symptoms of liver injury, or hypersensitivity e.g., fatigue, decreased appetite, nausea, vomiting, abdominal

Liver Chemistry Stopping Criteria	

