8.5.6. Liver Events

Number and percentage of subjects with liver events will be tabulated by study phase. Number and percentage of subjects with clinical significant hepatobiliary laboratory abnormalities during the study will also be tabulated. Full information of liver events will be listed.

Table 20 provides an overview of the planned liver event analyses, with full details of data displays being presented in Appendix 14: List of Data Displays.

Table 20 Overview of Planned Liver Event Analyses

Display Type	Data Displays Generated						
	Stats Analysis			Summary		Individual	
	T	F	L	T	F	F	L
Liver Event Analyses							
All liver events				Y			Y
Hepatobiliary laboratory abnormalities				Y			

NOTES:

- T = Table, F = Figure, L = Listing, Y = Yes display generated.
- Stats Analysis = Represents TFL related to any formal statistical analyses (i.e. modelling) conducted.
- Summary = Represents TFL related to any summaries (i.e. descriptive statistics) of the observed raw data.
- Individual = Represents FL related to any displays of individual subject observed raw data.

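### SAP 10.5.3 bars unscheduled visits from every summary table, which conflicts with the maximum-grade rule in SAP 7.1.3 and leaves the hepatobiliary table without the liver tests that the protocol requires off schedule.

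*SAP*

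**What the plan says.** The general rule is in SAP 10.5.3, under the unscheduled-visits item: "Unscheduled visits will not be included in summary tables". The same item excludes them from figures and adds "All unscheduled visits will be included in listings". Unlike other items in that section, it has no clause allowing for a different statement elsewhere. Both versions of the analysis plan in the SAP file carry this text.

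The laboratory rule is in SAP 7.1.3, in the paragraph on shift tables: "Data collected at unscheduled visits will not be included in the by-visit summary, but will be used in the calculation of maximum grade" per phase. The same section specifies the Grade 2 or higher table: "Grade 2 or higher laboratory events will be tabulated by number and percentage of subjects with the event by study phase". That sentence does not mention unscheduled data.

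SAP 8.5.6 specifies the hepatobiliary table: "Number and percentage of subjects with clinical significant hepatobiliary laboratory abnormalities during the study will also be tabulated". It has no rule on unscheduled data either.

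Protocol 10.3 sets the default for tabulated safety summaries, "only the scheduled assessments will be included in the summary tables", and goes on to allow the analysis plan to provide otherwise.

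Protocol Appendix 6 sets the follow-up once ALT reaches 3 times the upper limit of normal (ULN). If bilirubin or INR is also raised, liver chemistry is repeated within 24 hours, and then: "Monitor participants twice weekly until liver chemistries resolve, stabilize or return to within baseline". If ALT alone is raised, the repeat is within 24 to 72 hours and monitoring is weekly. INR is rechecked with each liver panel until transaminases turn down. Appendix 6 itself calls liver tests of this kind unscheduled.

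**The concern.** Off-schedule laboratory tests are mostly taken because something is already abnormal. Leaving them out of an any-time or worst-case table is therefore not neutral, because the values left out are the ones most likely to show the peak. Drug-induced liver injury is the first risk in the protocol's own risk table (Protocol 3.3.1), and the hepatobiliary table is where a reader would look for it.

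There is also a plain programming problem. The maximum-grade shift tables are themselves summaries by title, so 10.5.3 and 7.1.3 give opposite instructions for the same rows. If the two rules were applied to different tables, one man could appear at different worst grades within one report.

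**Working it through.** The documents give no figure on this point, so the check compares the rules table by table and then sets a scale.

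**1. Which rule governs which table**

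| Display | Time frame | Rule in its own section | With 10.5.3 |
|---|---|---|---|
| By-visit rows (2.18, 2.19, by-visit part of 2.21 to 2.23) | each scheduled visit | exclude (7.1.3) | agree |
| Maximum-grade rows of 2.21 to 2.23 | per phase | include (7.1.3) | direct conflict |
| Table 2.16, Grade 2 or higher | per phase | none explicit | ambiguous |
| Table 2.27, hepatobiliary | whole study | none | excluded by default |

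For Table 2.16, SAP 7.1 says that all injection-phase data from injected participants are analysed, and SAP 10.4.1 assigns assessments to phases by date. A Grade 2 or higher event within a phase is the same thing as a maximum grade of at least 2 in that phase. These points favour inclusion, but no sentence says so. For Table 2.27 nothing overrides 10.5.3 or the Protocol 10.3 default.

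**2. Direction of the effect**

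Let S be a man's scheduled results and A all his results. S is a subset of A, so max(S) ≤ max(A). A count of men at or above a threshold can therefore stay the same or fall when S is used. It cannot rise.

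**3. What would actually be missed**

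The DAIDS bands in Protocol Appendix 7 for ALT are 2.5 to <5 × ULN for Grade 2, 5 to <10 × ULN for Grade 3 and ≥10 × ULN for Grade 4. The 3 × ULN trigger is therefore already Grade 2. If it is seen at a scheduled visit, that man is counted in Table 2.16 under either rule. The losses are limited to:

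- escalation to Grade 3 or 4 seen only at follow-up;
- a bilirubin or INR abnormality found only at follow-up;
- a trigger value first seen at an unscheduled visit.

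**4. How much testing lies off schedule**

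In the Schedule of Activities, injection-phase chemistry is at Weeks 5, 6, 9, 17, 25, 33 and 41, giving gaps of 1, 3, 8, 8, 8 and 8 weeks. Weeks 10, 18, 26, 34 and 37 have none. If monitoring lasted a full 8-week gap:

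- weekly: 7 panels strictly inside the gap, 8 if the closing one is counted;
- twice weekly: 7 × 2 = 14 to 8 × 2 = 16 panels.

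These are upper bounds. Monitoring stops once values resolve or stabilise. A man who meets the ALT criterion also stops injections and moves to the follow-up calendar, so this visit grid is not exactly his.

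**5. Scale in the table**

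This illustration assumes one man who reaches a category only off schedule. The denominators are about 40 entering the injection phase and about 48 entering the oral phase (Protocol 5.2). Intervals are Clopper-Pearson. With x = 0 the upper limit is 1 − 0.025^(1/n), and with x = 1 the lower limit is 1 − 0.975^(1/n). The upper limit for x = 1 is the 97.5% quantile of Beta(2, n − 1).

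| n | Unscheduled excluded | Unscheduled counted |
|---|---|---|
| 40 | 0% (0 to 8.8%) | 2.5% (0.06 to 13.2%) |
| 48 | 0% (0 to 7.4%) | 2.1% (0.05 to 11.1%) |

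The SAP does not plan intervals for this table. They are shown only to convey what one man is worth at this sample size.

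**The case against.** The best defence is that a specific rule overrides a general one. Protocol 10.3 lets the analysis plan make exceptions, and SAP 7.1.3 makes one for maximum grade. On that reading the shift tables are safe, and with SAP 7.1 so, in all likelihood, is Table 2.16. This has force, but it leaves the contradiction in the text, and it does not reach Table 2.27, whose section contains no exception.

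The second defence is that little would be hidden. An ALT of 3 × ULN or more requires a liver event form, and liver events have their own table by phase (Table 2.26) and listing (Listing 36). ALT with raised bilirubin or INR meeting the Appendix 6 criteria is reported as an SAE and reaches the SAE tables. Clinically relevant laboratory changes are recorded as adverse events, and all values stay in the laboratory listings. This stands. The defect concerns summary rates and leaves the underlying data in the report.

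Three stronger readings are tempting, and the documents do not support them:

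- A reader might infer that exclusion always lowers the worst grade, or that an event found between visits drops out of the report. Neither follows: the grade may be unchanged, and the other displays remain.
- A reader might infer from the sparse INR schedule (Screening and Week 41) that Table 2.27 could show a combined ALT and INR category only at Week 41. The rows of that table come from a standard shell that is not in the documents, and the liver concern ranges in SAP 10.8.1 contain no INR.
- A reader might extend the point to the vital-sign shift table. Appendix 6 requires no off-schedule vital signs, so the argument from mandated follow-up does not carry over.

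**Conclusion.** The concern holds in a limited form. SAP 10.5.3 and 7.1.3 contradict each other for the maximum-grade rows of Tables 2.21 to 2.23. Table 2.16 is ambiguous but leans towards inclusion. Table 2.27, meant to cover the whole study, falls on the literal text to scheduled values only, although Protocol Appendix 6 requires the off-schedule tests most likely to show the peak.

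The bias runs in one direction, downward or nil, and with about 40 to 48 men each missed case is worth 2.1 to 2.5 percentage points. How many cases would be affected cannot be known from the documents and could be none. The conclusion assumes that 10.5.3 is applied as written and that the shell for Table 2.27, which is not available here, does not itself admit unscheduled values. The study is descriptive, so no test or power statement is affected. The change is worth making because the tables concern the main safety risk and the correction is trivial.

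**What to change.** Replace the sentence in SAP 10.5.3 with:

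> Unscheduled visits are excluded from by-visit summaries and figures only; all post-baseline results, scheduled or not, count in any-time and worst-case laboratory summaries (Table 2.16, the maximum-grade rows of Tables 2.21 to 2.23, and Table 2.27).

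Keep the listings sentence, and add a one-line cross-reference in 7.1.3 (for Table 2.16) and in 8.5.6 (for Table 2.27). This extends the principle that 7.1.3 already states, and Protocol 10.3 permits it because it leaves exceptions to the analysis plan.

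The cost is SAP wording and one derivation flag. No new data are collected. Reported abnormality rates may come out slightly higher.
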